8.1.1. Study Day Definition

- Study Day 1 is defined as the date of first dose for treated participants.
- Study Day will be calculated relative to the date of first dose for treated participants.

If event is prior to the first dose, then study day is calculated as:

Date of Event – Day 1

If event is after the first dose, then study day is calculated as:

Date of Event – Day 1 + 1

8.1.2. Missing Data

All subjects will be used in the analyses, as per the analysis sets, using all non-missing data available; Handling of missing or incomplete dates in AE is discussed in [Appendix B](#).

8.2. Background Characteristics

8.2.1. Participant Disposition

A disposition of all participants who enter the study will be provided, from screening to study completion. A completer of the study is a participant with the study completion question answered ‘Yes’ on the End of Study CRF page. A completer of treatment is a participant with the treatment completion question answered ‘Yes’ on the IP Completion (End of Treatment) CRF page. The primary reason for discontinuing the study is provided in the respective CRF page.

The summaries of participant disposition of all participants will include:

- Number of participants screened,
- Number of participants screen-failed,

- Number of participants enrolled,
- Number of participants enrolled but not received any IP,
- Number and percentage of participants received at least one dose of IP
- Number and percentage of participants who had dose interrupted
- Number and percentage of participants completed one-year IP
- Number and percentage of participants discontinued IP and primary reason for IP discontinuation
- Number and percentage of participants completed the one-year study
- Number and percentage of participants withdrawal from the study and primary reason for withdrawal from the study

All percentages will be calculated based on the participants in the Safety Set. If a participant is rescreened because the participant has been a screen failure the first time, the status of the participant will be determined from the second screening. In the count of screened participants, this participant will be counted only once.

By-participant listings of disposition details will also be provided.

The number of participants in each analysis set will be provided. A separate listing will be provided for the participant who did not meet inclusion/exclusion criteria but have received IP using Enrolled set.

A separate data listing will be provided for all participants who prematurely discontinued IP or prematurely withdrew from the study with any reason, number of days on IP, date of withdrawal from the study using Safety Set.

8.2.2. Protocol Deviations

Protocol deviations will be classified as “major” or “minor” on ongoing basis by the clinical study team and sponsor and documented separately from the SAP.

A by-participant listing of all protocol deviations will also be provided.

8.2.3. Demographics and Baseline Characteristics

This analysis will be based on the Safety Set.

Demographic characteristics (including age, race, sex, ethnicity, childbearing status, years of education, current employment status, and total years of employment) and baseline characteristics, such as height, weight, body mass index (BMI), will be summarized.

Baseline subgroups will be summarized for the following categories:

- Age (≤ 50 , > 50)
- Sex (Male, Female, Unknown/Undifferentiated)

By-participant listing of demographic and other baseline characteristics will also be provided.

8.2.4. Physical Examination

This analysis will be based on the Safety Set.

Only clinically significant abnormalities are captured in the database – for post-baseline observations, these will be reported as adverse events, hence these will be included in AE displays; for pre-baseline observations will not be reported.

The dates of physical examination will be listed to confirm that the examination was done.

8.2.5. Investigational Product Exposure

This analysis will be based on the Safety Set.

Listing of first and last day of IP intake, total period of IP intake, and dates and duration of IP interruption will be provided by participant.

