7.1.3. Treatment Period

Beginning on Day 1 and continuing through the Treatment Period, participants will self-administer investigational product (IP) once per day in the morning and will track IP intake in a participant diary. At clinic visits, participants will take the IP under staff supervision, followed by assessments [REDACTED]

[REDACTED]. Study staff will dispense sufficient IP for daily administration until the next scheduled study visit.

Adherence to the dosing regimen will be assessed at each in-clinic visit by examination of the used packaging, counting any returned capsules, and reviewing the participant diary. Participants should continue to self-administer IP within the visit window up until the Month 48 Visit.

7.1.3.1. Additional visits related to the transition from Protocol Version 2 to Protocol Version 3

Participants who have completed Day 395 under Protocol Version 2 (“718-CIH-301 v2 Completers”)

Participants who have completed their Day 395 visit under Protocol Version 2 and wish to continue participation under Protocol Version 3 or higher (“718-CIH-301 v2 Completers”) will return to the site for a Re-Qualification Visit ([Table 4](#)) up to 28 days prior to resuming IP at their Next Scheduled Study Treatment Visit (relative to the date of their Day 1 visit, see [Table 5](#)). Participants must sign an ICF for Protocol Version 3 or higher prior to any further study procedures. Inclusion criteria #1-11 (Section [8.1](#)) and exclusion criteria #1-17 and #20-22 (Section [8.2](#)) will be re-confirmed at this visit and documented appropriately. Exclusion criteria #17 should be re-confirmed for both Cohort 1 and Cohort 2 participants. Exclusion criteria #2, #5, and #8 should be assessed at or relative to the time of the Re-Qualification Visit. Exclusion criteria #21 should be assessed relative to initial participation in 718-CIH-301 under Protocol Version 2 or prior.

718-CIH-301 v2 Completers will resume IP at their Next Scheduled Study Treatment Visit (see [Table 5](#)). The Next Scheduled Study Treatment Visit may be any visit within the Treatment Period and will depend on the participant’s visit schedule, which will remain relative to the date of their Day 1 visit.

Thirty (30) days after resuming IP at their Next Scheduled Study Treatment Visit ([Table 5](#)), 718-CIH-301 v2 Completers will return to the site for a Post Re-Qualification Safety Check-in visit to evaluate safety ([Table 4](#)).

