2. INTRODUCTION

This statistical analysis plan (SAP) is for the final analysis for study protocol SAGE-718-CIH-301 and is based on the following approved study documents:

- Study Protocol v3.0, Amendment 2 (05 February 2024)
- electronic Case Report Form (eCRF), Version 7.0 (11 December 2024)

Due to results in Dimension (718-CIH-201) investigating SAGE-718, a decision was made on November 20, 2024, to prematurely terminate the 718-CIH-301 study. A synoptic clinical study report (CSR) will be produced. This SAP describes the analyses performed for the synoptic CSR, which will be purely descriptive and focused on primary endpoints only. All analyses and data presentations will be generated using SAS® Version 9.4 or higher Software (SAS Institute, Cary, North Carolina, USA). This SAP will be finalized and approved before the clinical database lock. Any changes made to the SAP after the clinical database lock will be documented and discussed in the CSR for this study.

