Protocol amendment 2 allowed the duration of participation to be extended from up to 1 year to up to 4 years and provided a path to resume treatment for participants who completed study (through Day 395 visit) under Protocol Version 2 ("718-CIH-301 v2 Completers") or

completed treatment (through Day 365 visit) but did not yet have a Day 395 visit. Participants who have completed their Day 395 visit under Protocol Version 2 and wish to continue participation under Protocol Version 3 or higher ("718-CIH-301 v2 Completers") will return to the site for a Re-Qualification Visit up to 28 days prior to resuming IP at their Next Scheduled Study Treatment Visit (relative to the date of their Day 1 visit. Relevant inclusion and exclusion criteria will be re-confirmed at the Re-Qualification Visit, and participants will re-consent to study participation prior to continuing in the study. Thirty (30) days after resuming IP at their Next Scheduled Study Treatment Visit, 718-CIH-301 v2 Completers will return to the site for a Post Re-Qualification Safety Check-in visit to evaluate safety.

Participants who have completed their Day 365 visit but not their Day 395 visit under Protocol Version 2 when Protocol Version 3 or higher is implemented will NOT be considered "718-CIH-301 v2 Completers". Instead, these participants will return to the site as soon as possible for a Study Continuation Visit during which they will consent to Protocol Version 3 or higher, complete safety assessments, and be dispensed SAGE-718 to resume study treatment. They will continue their study visits per in [Table 3](#) and will not have a Day 395 visit.

Figure 1: Study Schematics

Abbreviation: [REDACTED]

^a De novo and gap (>7 days) rollover participants only. For direct (≤7 days) rollover participants, results of selected last parent study assessment to be used as Day 1 assessments when applicable.

^b The Safety Follow-Up Visit will take place 30 days (±7 days) after the Month 48 or ET visit.

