8. STATISTICAL ANALYSIS

8.1. General Considerations

Continuous data will be summarized with the number of participants (n), mean, standard deviation (SD), minimum, and maximum. The minimum and maximum will be reported to the same number of decimal places as the raw data recorded in the database. The mean and median will be reported to one more decimal place, and the SD (and the standard error [SE], if applicable) will be reported to two more decimal places, than the raw data recorded in the database. In general, the maximum number of decimal places reported will be four for any summary statistic. Any values that require transformation to standard units (metric or SI) will be converted with the appropriate corresponding precision.

Categorical data will be summarized with the number of participants providing data at the relevant time point (n), frequency counts and percentages. Percentages will be reported to one decimal place unless otherwise specified. Any planned collapsing of categories will be detailed in the SAP text and the data displays.

Percentages will not be presented for zero counts. Percentages will be calculated using the number of participants (n) in the respective analysis set as the denominator. A missing category shall be included only for categorical variables where no data is available. The missing category will be omitted if there are no missing values for that variable.

For the laboratory results that are “ $\leq x$ ” or “ $\geq x$ ”, where x is a number as collected in the data, the numeric part of the result will be used in the calculation in the summary tables. If a laboratory value contains ‘y <’ then y minus 0.1 for values measured to the first decimal place, 0.01 for values measured to the second place, 0.001 for values measured to the third decimal place, and so on, will be used for the analysis. If a laboratory value contains ‘z >’ then z plus 0.1 for values measured to the first decimal place, 0.01 for values measured to the second place, 0.001 for values measured to the third decimal place, and so on, will be used for the analysis. The same is true if the result is presented as below limit of quantification (BLQ) and a lower limit of quantification (LLOQ) value is provided – LLOQ value will be used for calculation in the summary tables. The actual results as collected will be displayed in the listings.

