The analysis of AEs will be based on the concept of TEAEs. If the date of an adverse event is incomplete and an unambiguous determination could not be made with respect to its onset time versus the first dose of study drug and/or last dose of study drug, the adverse event will be assumed to be a TEAE. For imputation of missing AE dates, please refer to [Appendix B](#).

An overall summary of TEAEs will include the number and percentage of participants in the following categories:

- Any TEAEs
- Any TEAEs (Pre-treatment, On-treatment, Post-treatment)
- TEAEs by maximum Severity (severe>moderate>mild)
- Any TEAEs related to IP
- Any TEAEs leading to death
- Any TEAEs leading to IP discontinuation
- Any TEAEs leading to withdrawal from the study
- Any TEAEs leading to IP interruption
- Any serious TEAEs
- Any serious TEAE related to IP

- Any serious TEAE leading to IP discontinuation
- Any serious TEAE leading to withdrawal from the study

Incidence of TEAEs in following categories will be provided by System Organ Class (SOC) and Preferred Term (PT). A participant is counted only once under each SOC and PT in case of multiple occurrences of the same AE. These tables will be sorted by decreasing frequency of SOC in overall group, then alphabetically first within SOC then within PT.

- Any TEAE
- TEAEs by maximum severity
- TEAEs by relationship
- Serious TEAEs
- TEAEs leading to IP discontinuation
- TEAEs leading to withdrawal from the study
- TEAEs leading to IP interruption

Additionally, incidence of TEAEs will be summarized by PT. Most common TEAEs reported >5% in any cohort will also be summarized by PT.

For maximum severity, participants will be counted only once within each SOC and PT at the maximum severity in the following order: severe > moderate > mild; an AE with missing severity will be omitted from severity presentation and will not be imputed. For relationship to IP, participant will be counted only once within each SOC and PT at the strongest relationship to IP in the following order: related > not related; an AE with relationship missing is treated as related. For seriousness, an AE with missing seriousness will not be included in the summary tables. The incidences will be sorted by descending frequency of SOC and then, within a SOC, by descending frequency of PT based on overall group, and in alphabetical order of PT if the incidence within a PT is a tie.

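### TEAEs are tabulated only as n (%) and time on drug is only listed, and the on-treatment window has no rule for the off-drug gap of Version 2 completers who resume

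*SAP*

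**What the plan says.** SAP 8.3.1 states: "An overall summary of TEAEs will include the number and percentage of participants in the following categories". The tables by system organ class and preferred term are participant incidences too. SAP 8.1 fixes the denominator: "Percentages will be calculated using the number of participants (n) in the respective analysis set as the denominator". No person-time, event rate or time-to-event summary is planned.

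For exposure, SAP 8.2.5 provides a "Listing of first and last day of IP intake, total period of IP intake, and dates and duration of IP interruption" for each participant. SAP 8.2.1 tabulates how many had a dose interruption, completed one year of drug, or discontinued it, and lists days on drug for those who stopped early.

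Several features make time on drug unequal. SAP 5.1 records that "Protocol amendment 2 allowed the duration of participation to be extended from up to 1 year to up to 4 years". Protocol 7.1.3.1 says that "718-CIH-301 v2 Completers will resume IP at their Next Scheduled Study Treatment Visit", so they have a period off drug after Day 365. Participants who had passed Day 365 but not Day 395 attend a Study Continuation Visit to "be dispensed SAGE-718 to resume study treatment". Finally, SAP Section 2 reports that "a decision was made on November 20, 2024, to prematurely terminate the 718-CIH-301 study".

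SAP 8.3.1 defines an on-treatment TEAE by one start (first dose) and one end (last dose plus 30 days), and a post-treatment TEAE as onset from 31 days after the last dose. Under SAP Appendix A, Table 7, footnotes f and o, new events after Day 395 and before Version 3 consent go to interim medical history, and AE collection restarts at that consent.

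**The concern.** The objective is long-term safety. The percentage of participants with a TEAE rises with the time they are observed, so a reader needs that time to interpret it. Here the percentage pools people who stopped at one year, people who went on or came back, and people cut off by the termination. TEAEs are counted to the end of the study, whatever visits the other summaries use. With exposure only in a listing, no table tells the reader over what period the percentage arose.

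The second issue is a label. A window with a single start and a single end treats a participant who stopped, was off drug for months and then resumed as continuously on treatment. An AE in the off-drug weeks just before resumption is on-treatment if the participant later resumes. If the participant never resumes, the same AE is post-treatment once it is 31 or more days after the last dose. The label thus depends on what happens afterwards.

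**Working it through.** The documents state no exposure total and no event rate, so there is no planned figure to reproduce.

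**1. How far exposure can differ.** Protocol Version 3.0 is dated 5 February 2024 and the termination decision 20 November 2024, which is 289 days later. Assume nobody took drug past Day 365 before Version 3. Time on drug at the decision was then at most about 365 + 289 = 654 days. Anyone first dosed after 22 November 2023 (20 November 2024 minus 364 days) had not reached Day 365. These are limits from dates, not observed exposure; no first-dose dates are given.

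**2. What unequal time does to a percentage.** Illustration only, because the documents give no rate. With a constant first-event rate λ per person-year, the expected percentage after t years is 1 − exp(−λt).

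| Assumed λ | 6 months | 18 months |
|---|---|---|
| 0.25 | 11.8% | 31.3% |
| 0.5 | 22.1% | 52.8% |
| 1.0 | 39.3% | 77.7% |

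The underlying risk per unit time is the same across each row; only the time differs.

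**3. The Version 2 completer gap.** Inputs: last Version 2 dose on Day 365 (assumed, at the target day); resumption day R from SAP Table 3; re-consent at the earliest, 28 days before R; Day 395 visit on target.

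| Resumes at | R | Dose-free days (R − 366) | Of these, more than 30 days after the stop (R − 396) | Days from last dose to earliest re-consent (R − 28 − 365) | Days without AE collection, at least (R − 28 − 396) |
|---|---|---|---|---|---|
| Month 15 | 456 | 90 | 60 | 63 | 32 |
| Month 18 | 547 | 181 | 151 | 154 | 123 |
| Month 21 | 638 | 272 | 242 | 245 | 214 |
| Month 24 | 730 | 364 | 334 | 337 | 306 |

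**4. Tightest case allowed by the visit windows.** Day 365 visit 14 days late (Day 379), Month 15 visit 14 days early (Day 442), re-consent on Day 442 − 28 = 414. Re-consent is then 414 − 379 = 35 days after the last dose, still more than 30. With the Day 395 visit on Day 402 (the ±7 days in Protocol 20.2), the days without AE collection are 403 to 413, which is 11.

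**5. How many AEs can be mislabelled.** Only those with onset between re-consent and resumption, at most 28 days per Version 2 completer who resumes. Events from Day 395 to re-consent are medical history and enter no TEAE table. The on-treatment label is used in one place, the pre-/on-/post-treatment row of the overall TEAE summary. The other TEAE tables use all TEAEs.

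**6. Study Continuation participants.** With the visit as late as Day 402 and last dose on Day 365, there are up to 402 − 365 − 1 = 36 dose-free days, or 402 − 351 − 1 = 50 if the Day 365 visit was on Day 351. This matters for counting days on drug.

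**The case against.** The case for leaving the SAP alone is substantial. The proportion is the endpoint in both documents, and the protocol promises no exposure table. The SAP serves a synoptic report after early termination, and SAP 6.1 openly narrows it to primary endpoints at a few visits. There is no comparator, so unequal exposure biases no treatment contrast. Exposure is listed for every participant, and some related counts are tabulated. All of this stands, and it makes the point an improvement rather than a correction of an error. It does not supply what is missing: a long-term safety percentage still appears without a summary of the time behind it, although the dates are to be listed.

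Some stronger readings are tempting, but the documents do not support them:

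- A reader might infer that the window spanning the gap inflates the SAP's exposure or dilutes its rates. The SAP uses no person-time denominator, so nothing planned is distorted in that way. The gap would matter for person-time only if a rate were added without removing it.
- A reader might infer that many off-drug events are counted as on-treatment. Step 5 shows that only a short period per participant, and one row, is affected.
- A reader might infer that the one-year completer row miscounts, because SAP 8.2.1 defines completion by a CRF answer while the protocol's Treatment Period now runs to Month 48. The eCRF is not among the documents, so this cannot be shown.
- A reader might infer that nothing is recorded during the gap. New or worsening conditions go to interim medical history, and Protocol 12.2.6 keeps related SAEs after follow-up reportable.

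**Conclusion.** The point holds as a cheap improvement. That time on drug differs follows from the design; its spread is unknown, because no first-dose dates or numbers of resuming participants are given. The percentages in step 2 rest on assumed constant rates and show only the direction and possible scale.

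The gap in the on-treatment definition is real as written. It holds even under the least favourable visit windows, where mislabelling starts 35 days after the last dose against an allowance of 30 (63 days or more at target days). Its practical effect is small: one row, at most about 28 days of AE collection per resuming Version 2 completer, and probably few events. The minima of 63 days off drug and 32 days without AE collection apply at target days only; with adverse windows they fall to 35 and 11. Cohort 3 was not enrolled (SAP 6.1), so this concerns Cohorts 1 and 2 and the overall column.

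**What to change.** 1. **SAP 8.2.5.** Add an exposure table by cohort and overall: mean, median and range of days on drug, total person-years, and the number exposed for at least 3, 6, 12 and 18 months. Count days net of interruptions and of any off-drug gap at the Version 2 to Version 3 transition. Derive the 12-month count from dosing dates with a stated threshold, for example 365 days, or 351 to allow for the −14-day visit window.
2. **SAP 8.3.1, labelling.** For analysis, define on-treatment as each dosing period plus 30 days. State how an AE with onset between re-consent and resumption is labelled. It remains a TEAE and stays in n (%).
3. **SAP 8.3.1, rates.** Beside n (%), add descriptive exposure-adjusted incidence rates for any TEAE, serious TEAEs and TEAEs leading to discontinuation of drug. Use the same at-risk period in numerator and denominator: time on drug plus 30 days after each stop, up to the first event. Exclude later off-drug time.

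The cost is a few tables and the derivation of separate dosing periods, from dates that SAP 8.2.5 already plans to list. The rates assume a roughly constant hazard, so they understate early risk if first events cluster early, and they do not account for SAGE-718 taken in the parent study. They supplement the proportion and do not replace it. SAP Section 2 allows the change before database lock, or afterwards if documented in the study report.
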